## 6.2 Second Course Treatment

Trial Period:	Screening Phase	Treatment Cycles (3-week Cycles)								End of Treatment	Post-Treatment		
Treatment Cycle/Title:	Screening	1	2	3	4	To be repeated beyond 8 cycles				Discon	Safety Follow-up	Follow Up Visits	Survival Follow-Up a
						5	6	7	8				
Scheduling Window (Days)b:	-28 to -1		± 3	± 3	± 3	± 3	± 3	± 3	± 3	At time of Discon	30 days post last dose	Every 8 weeks post discon	Every 12 weeks
Administrative Procedures													
Eligibility Criteria	X												
Concomitant Medication Review	X	X	X	X	X	X	X	X	X	X	X		
Clinical Procedures/Assessments													
Review Adverse Events c	X	X	X	X	X	X	X	X	X	X	X c		
Full Physical Examination	X									X			
Directed Physical Examination		X	X	X	X	X	X	X	X				
Weight and Vital Signs (T, P, RR, BP)	X	X	X	X	X	X	X	X	X	X			
ECOG Performance Status e	X	X	X	X	X	X	X	X	X	X			
Post-study Anticancer Therapy Status											X	X	X
Survival Status a													X
Laboratory Procedures/Assessments: analysis performed by LOCAL laboratorym													
Pregnancy Test – Urine or Serum β-HCG f	X												

Trial Period:	Screening Phase	Treatment Cycles (3-week Cycles)								End of Treatment	Post-Treatment			
Treatment Cycle/Title:	Screening	1	2	3	4	To be repeated beyond 8 cycles				Discon	Safety Follow-up	Follow Up Visits	Survival Follow-Up a	
Scheduling Window (Days) b :	-28 to -1		± 3	± 3	± 3	± 3	± 3	± 3	± 3	± 3	At time of Discon	30 days post last dose	Every 8 weeks post discon	Every 12 weeks
PT/INR and aPTT g,h	X e		X		X		X		X	X				
CBC with Differential g	X e		X	X	X	X	X	X	X	X		X		
Chemistry and Liver Panel g	X e		X	X	X	X	X	X	X	X		X		
Urinalysis g,h	X e		X		X		X		X	X				
T3, FT4 and TSH g,h	X e		X		X		X		X	X				
Efficacy Assessment														
CT Chest/Abdomen/Pelvis i	X								X i	X j			X	
Bone Scan k	X								X k					
Brain Imaging l	X								X l					
CENTRAL Laboratory Assessments														
Archival or Newly Obtained Tissue Collection	X									X n				
Correlative Studies Blood Collection m	X			X					X	X				

- a. In subjects who experience PD or starts a new anti-cancer therapy contact should be made (example: by telephone) approximately Q12W to assess for survival status. Updated survival status may be requested by the Sponsor at any time during the course of study. Upon Sponsor notification, all participants who do not/will not have a scheduled study visit or study contact during the Sponsor defined time period will be contacted for their survival status (excluding participants that have a death event previously recorded).
- b. Cycle 1 treatment must be given within 3 days of treatment allocation. The window for each visit is  $\pm 3$  days unless otherwise noted. If dosing is delayed due to administrative reasons, the subsequent dosing visit should be re-calculated to account for the every 3 week dosing visit.
- c. SAEs will be followed through 90 days following cessation of treatment, or 30 days following cessation of treatment if the subject initiates a new anticancer therapy, whichever is earlier. All protocol specific ECIs will be collected throughout the study as listed in Section 7.2.3.2. If any of the ECI criteria are met, collect the details until the ECIs resolve.
- d. Height will be measured at screening only.
- e. ECOG Performance Status and laboratory test for screening and determining eligibility are to be performed within 10days prior of the first dose of trial treatment except thyroid test, which may performed within 28days.
- f. For women of reproductive potential, a serum pregnancy test should be performed within 72 hours prior to receiving the first dose of study medication (Cycle 1 Day 1). Subject must be excluded/discontinued in the event of a positive results.
- g. After Cycle 1, laboratory samples can be collected up to 72 hours prior to the scheduled time point. CBC with differential, chemistry panel and liver panel to be performed every cycle. Details can be found in Section 7.1.3 Laboratory Procedure/Assessments. Liver panel to include albumin, ALT, AST, total bilirubin, alkaline phosphatase and total protein.
- h. While on treatment, PT/INR and aPTT, UA and thyroid function tests will be performed every other cycle.
- i. Screening tumour imaging will be performed within 28 days prior to treatment allocation. Imaging at screening should include chest, abdomen, and pelvis. The first on-study imaging time point will be performed at 9 week ( $\pm 7$  days) calculated from the date of treatment allocation and will be continue to be performed Q9W ( $63\pm 7$  days) in the first year, Q12W ( $84\pm 7$ days) in the second year of therapy.
- j. If previous imaging was obtained within 4 weeks prior to the date of discontinuation, then imaging at treatment discontinuation is not mandatory.
- k. Only for those with a history of bone metastases, to be repeated Q9W ( $63\pm 7$  days) from treatment allocation in first year, Q12W ( $84\pm 7$ days) in second year of therapy.
- l. Only for those with known brain metastases, CT or MRI brain to be repeated Q9W ( $63\pm 7$  days) from treatment allocation in first year, Q12W ( $84\pm 7$ days) in second year of therapy.
- m. Blood for correlative studies should be collected at Cycle 3, at Cycle 6 and again at discontinuation (end of treatment).
- n. Tissue collection through core needle biopsy (CNB) or excisional biopsy (EB) may be performed when progressive disease is confirmed.

## **7.0 TRIAL PROCEDURES**

### **7.1 Trial Procedures**

This study has a pre-screening genetic testing to confirm the participant's APOBEC3B germline mutation status. Participant with a confirmed APOBEC3B germline mutation will proceed to the main screening of the study. The Trial Flow Chart - Section 6.0 summarizes the trial procedures to be performed at each visit (including screening visit). Individual trial procedures are described in detail below. It may be necessary to perform these procedures at unscheduled time points if deemed clinically necessary by the investigator. Furthermore, additional evaluations/testing may be deemed necessary by the Sponsor and/or Merck for reasons related to participant safety.

#### **7.1.1 Administrative Procedures**

##### **7.1.1.1 Informed Consent**

The Investigator must obtain documented consent from each potential participant prior to participating in a clinical trial.

###### **7.1.1.1.1 General Informed Consent**

Consent must be documented by the participant's dated signature or by the participant's legally acceptable representative's dated signature on a consent form along with the dated signature of the person conducting the consent discussion.

A copy of the signed and dated consent form should be given to the participant before participation in the trial.

The initial informed consent form, any subsequent revised written informed consent form and any written information provided to the participant must receive the IRB/ERC's approval/favorable opinion in advance of use. The participant or his/her legally acceptable representative should be informed in a timely manner if new information becomes available that may be relevant to the participant's willingness to continue participation in the trial. The communication of this information will be provided and documented via a revised consent form or addendum to the original consent form that captures the participant's dated signature or by the participant's legally acceptable representative's dated signature.

The informed consent will adhere to IRB/ERC requirements, applicable laws and regulations and Sponsor requirements.

There are two sets of informed consents forms to be used in this study. The first informed consent form will be provided to all participants to participant in genetic testing to confirm their APOBEC3B germline mutation status at pre-screening. Participants with confirmed APOBEC3B germline mutation will then be provided the second informed consent form to participant in the main study.

### **7.1.1.2 Inclusion/Exclusion Criteria**

All inclusion and exclusion criteria will be reviewed by the investigator or qualified designee to ensure that the participant qualifies for the trial.

### **7.1.1.3 Medical History**

A medical history will be obtained by the investigator or qualified designee. Medical history will include all active conditions, and any condition diagnosed within the prior 10 years that are considered to be clinically significant by the Investigator. Details regarding the disease for which the participant has enrolled in this study will be recorded separately and not listed as medical history.

### **7.1.1.4 Prior and Concomitant Medications Review**

#### **7.1.1.4.1 Prior Medications**

The investigator or qualified designee will review prior medication use, including any protocol-specified washout requirement, and record prior medication taken by the participant within 28 days before starting the trial. Treatment for the disease for which the participant has enrolled in this study will be recorded separately and not listed as a prior medication.

#### **7.1.1.4.2 Concomitant Medications**

The investigator or qualified designee will record medication, if any, taken by the participant during the trial. All medications related to reportable SAEs and ECIs should be recorded as defined in Section 7.2.

### **7.1.1.5 Disease Details and Treatments**

#### **7.1.1.5.1 Disease Details**

The investigator or qualified designee will obtain prior and current details regarding disease status.

#### **7.1.1.5.2 Prior Treatment Details**

The investigator or qualified designee will review all prior cancer treatments including systemic treatments, radiation and surgeries.

#### **7.1.1.5.3 Subsequent Anti-Cancer Therapy Status**

The investigator or qualified designee will review all new anti-neoplastic therapy initiated after the last dose of trial treatment. If a participant initiates a new anti-cancer therapy within 30 days after the last dose of trial treatment, the 30 day Safety Follow-up visit must occur before the first dose of the new therapy. Once new anti-cancer therapy has been initiated the participant will move into survival follow-up.

#### **7.1.1.6 Assignment of Allocation Number**

All consented subjects will be given a unique allocation number that will be used to identify the subject for all procedures that occurring prior and after treatment allocation. Each subject will be assigned only one allocation number. Allocation numbers must not be re-used for different subjects.

A single subject cannot be assigned more than 1 allocation number.

#### **7.1.1.7 Trial Compliance (Medication/Diet/Activity/Other)**

Interruptions from the protocol specified treatment plan for greater than 12 weeks between doses for non-drug-related or administrative reasons require consultation between the investigator and the Sponsor and written documentation of the collaborative decision on subject management.

The total volume of study treatment infused will be compared to the total volume prepared to determine compliance with each dose administered. The instructions for preparing and administering study treatment are provided in the Pharmacy Manual.

Administration of trial medication will be witnessed by the investigator and/or trial staff or qualified designee per institutional guidelines and procedures.

### **7.1.2 Clinical Procedures/Assessments**

#### **7.1.2.1 Adverse Event (AE) Monitoring**

The investigator or qualified designee will assess each participant to evaluate for potential new or worsening AEs as specified in the Trial Flow Chart and more frequently if clinically indicated. Adverse experiences will be graded and recorded throughout the study and during the follow-up period according to NCI CTCAE Version 4.0 (see Appendix 2). Toxicities will be characterized in terms regarding seriousness, causality, toxicity grading, and action taken with regard to trial treatment.

Please refer to section 7.2 for detailed information regarding the assessment and recording of AEs.

#### **7.1.2.2 Full Physical Exam**

The investigator or qualified designee will perform a complete physical exam during the screening period. Clinically significant abnormal findings should be recorded as medical history. A full physical exam should be performed during screening,

#### **7.1.2.3 Directed Physical Exam**

For cycles that do not require a full physical exam per the Trial Flow Chart, the investigator or qualified designee will perform a directed physical exam as clinically indicated prior to trial treatment administration.

#### **7.1.2.4 Vital Signs**

The investigator or qualified designee will take vital signs at screening, prior to the administration of each dose of trial treatment and at treatment discontinuation as specified in the Trial Flow Chart (Section 6.0). Vital signs should include temperature, pulse, respiratory rate, weight and blood pressure. Height will be measured at screening only.

#### **7.1.2.5 Eastern Cooperative Oncology Group (ECOG) Performance Scale**

The investigator or qualified designee will assess ECOG status (see Appendix 1) at screening, within 10 days prior to the administration of each dose of trial treatment and discontinuation of trial treatment as specified in the Trial Flow Chart.

#### **7.1.2.6 Tumour Imaging and Assessment of Disease**

Tumour imaging is strongly preferred to be acquired by computed tomography (CT). For the abdomen and pelvis, contrast-enhanced magnetic resonance imaging (MRI) may be used when CT with iodinated contrast is contraindicated, or when local practice mandates it. MRI is the preferred modality for imaging the brain. The same imaging technique regarding modality, ideally the same scanner, and the use of contrast should be used in a participant throughout the study to optimize the reproducibility of the assessment of existing and new tumour burden and improve the accuracy of the assessment of response or progression based on imaging.

Expedited confirmation of measurable disease based on RECIST 1.1 at screening should be used to determine participant eligibility. Confirmation that the participant's imaging shows at least 1 lesion that is appropriate for selection as a target lesion per RECIST 1.1 is highly recommended prior to participant allocation.

Participant eligibility will be determined using local assessment (Investigator assessment) based on RECIST 1.1. In addition, images (including via other modalities) that are obtained at an unscheduled time point to determine disease progression, as well as imaging obtained for other reasons, but which demonstrate radiologic progression, should also be used to determine progression.

When the Investigator identifies radiographic progression per RECIST 1.1, efforts should be made to verify radiologic PD. Treatment should continue until PD has been verified. Regardless of whether PD is verified, if the Investigator considers the participant has progressed, but elects to implement iRECIST, the Investigator will assess for confirmation of progression by iRECIST at subsequent time points.

##### **7.1.2.6.1 Initial Tumour Imaging**

Initial tumour imaging at Screening must be performed within 28 days prior to the date of treatment allocation. The site study team must review screening images to confirm the participant has measurable disease per RECIST 1.1.

The screening images must be reviewed by dedicated trial radiologists for measurable disease per RECIST 1.1 for eligibility prior to allocation.

Brain imaging, if performed to document the stability of existing metastases, should be by MRI if possible. CT with contrast is an acceptable alternative.

#### **7.1.2.6.2 Tumour Imaging During the Study**

The first on-study imaging assessment should be performed at 9 weeks ( $\pm 7$  days) from the date of treatment allocation. Subsequent tumour imaging should be performed every 9 weeks ( $\pm 7$  days) or more frequently if clinically indicated. After 52 weeks ( $\pm 7$  days), participants who remain on treatment will have imaging performed every 12 weeks ( $\pm 7$  days). Imaging timing should follow calendar days and should not be adjusted for delays in cycle starts. Imaging should continue to be performed until disease progression is identified by the Investigator.

Per iRECIST (Section 9.2.1.6), disease progression should be confirmed by the site 4 to 8 weeks after first radiologic evidence of PD in clinically stable participants. Participants who have unconfirmed disease progression may continue on treatment at the discretion of the Investigator until progression is confirmed by the site provided they have met the conditions detailed in Section 9.2.1.6. Participants who receive confirmatory imaging do not need to undergo the next scheduled tumour imaging if it is less than 4 weeks later; tumour imaging may resume at the subsequent scheduled imaging time point, if clinically stable. Participants who have confirmed disease progression by iRECIST, as assessed by the site, will discontinue study treatment. Exceptions are detailed in Section 9.2.1.6.

#### **7.1.2.6.3 End of Treatment and Follow-up Tumour Imaging**

In participants who discontinue study treatment, tumour imaging should be performed at the time of treatment discontinuation ( $\pm 4$  week window). If previous imaging was obtained within 4 weeks prior to the date of discontinuation, then imaging at treatment discontinuation is not mandatory. In participants who discontinue study treatment due to documented disease progression and the Investigator elects not to implement iRECIST, this is the final required tumour imaging.

In participants who discontinue study treatment without documented disease progression, every effort should be made to continue monitoring their disease status by tumour imaging using the same imaging schedule used while on treatment (every 9 weeks in Year 1 or every 12 weeks after Year 1) to monitor disease status until the start of a new anticancer treatment, disease progression, pregnancy, death, withdrawal of consent, or the end of the study, whichever occurs first.

#### **7.1.2.6.4 Second Course (Retreatment) Tumour Imaging**

Tumour imaging must be performed within 28 days prior to restarting treatment with pembrolizumab. Local reading (Investigator assessment with site radiology reading) will be used to determine eligibility.

The first on-study imaging assessment should be performed at 9 weeks ( $\pm 7$  days) after the restart of treatment. Subsequent tumour imaging should be performed every 12 weeks ( $\pm 7$  days) or more frequently, if clinically indicated.

Per RECIST 1.1 (Section 9.1.2.6), if tumour imaging shows initial PD, tumour assessment should be repeated 4 to 8 weeks later in order to confirm PD with the option of continuing treatment while awaiting radiologic confirmation of progression. Participants who obtain confirmatory imaging do not

need to undergo scheduled tumour imaging if it is less than 4 weeks later and may wait until the next scheduled imaging time point, if clinically stable.

Imaging should continue to be performed until disease progression, the start of a new anticancer treatment, withdrawal of consent, death, or notification by the Sponsor, whichever occurs first. Disease progression may be confirmed 4 to 8 weeks after the first tumour imaging indicating PD, by the Investigator using iRECIST, in clinically stable participants.

In participants who discontinue study treatment, tumour imaging should be performed at the time of treatment discontinuation ( $\pm 4$  week window). If previous imaging was obtained within 4 weeks prior to the date of discontinuation, then imaging at treatment discontinuation is not mandatory. In participants who discontinue study treatment due to documented disease progression, this is the final required tumour imaging.

In participants who discontinue study treatment without documented disease progression, every effort should be made to continue monitoring their disease status by radiologic imaging every 9 weeks ( $\pm 7$  days) until either the start of a new anticancer treatment, disease progression, pregnancy, death, or the end of the study, whichever occurs first.

#### **7.1.2.6.5 RECIST 1.1 Assessment of Disease**

RECIST 1.1 will be used as the primary measure for assessment of tumour response, date of disease progression, and as a basis for all protocol guidelines related to disease status (eg, discontinuation of study treatment).

#### **7.1.2.6.6 iRECIST Assessment of Disease**

iRECIST is based on RECIST 1.1, but adapted to account for the unique tumour response seen with immunotherapeutic drugs. When clinically stable, participants should not be discontinued until progression is confirmed by the Investigator, working with local radiology, according to the rules below. This allowance to continue treatment despite initial radiologic PD takes into account the observation that some participants can have a transient tumour flare in the first few months after the start of immunotherapy, and then experience subsequent disease response.

[figure not shown]
A description of the adaptations and iRECIST process is provided in Appendix 4, with additional detail in the iRECIST publication [Seymour et al, 2017]. iRECIST will be used by the Investigator to assess tumour response and progression, and make treatment decisions.

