**1.0 TRIAL SUMMARY**

Abbreviated Title	Pembrolizumab in metastatic HER2-negative breast cancer patients with APOBEC3B germline deletion polymorphism
Trial Phase	Phase II
Clinical Indication	Breast cancer
Trial Type	Intervention
Type of control	Single arm (no control/placebo group)
Route of administration	IV
Trial Blinding	Not applicable
Treatment Groups	Pembrolizumab: 200 mg intravenously every 3 weeks (Q3W)
Number of trial participants	Approximately 44 subjects will be enrolled
Estimated enrollment period	Mar 2019 - Apr 2021
Estimated duration of trial	4 years
Duration of Participation	2 years
Estimated average length of treatment per patient	
Each participate in the study from the time the subject signed the informed consent form through the final protocol specific contact. After screening phase of up to 28 days, eligible subjects will receive assigned treatment. Study treatment will continue for 35 administrations of pembrolizumab until any of the following occurs:
 
 
• disease progression, as defined by Response Evaluation Criteria in Solid Tumour version 1.1 (RECIST 1.1) (or progressive disease [PD] is confirmed, subject may be further followed up using consensus guideline of modified RECIST 1.1 [iRECIST] criteria);
 
• unacceptable toxicity;
 
• intercurrent illness that necessitates discontinuation of study treatment;
 
• Investigator’s decision to withdraw the subject,
 
• pregnancy,
 
• non-compliance with study treatment or procedure requirements;
 
• withdrawal of consent to treatment;
 
• death;
 
• end of the study, or
 
• other administrative reasons requiring cessation of study treatment.
 
 
After discontinuation of all study treatments, each subject will be followed for 30 days for AE and for 90 days for serious adverse events (SAEs) monitoring, as well as 12 weekly survival follow up using telephone call till end of study period.

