## 2.0 TRIAL DESIGN

This is an open label investigator initiated Phase II study of single agent pembrolizumab (Keytruda®) in metastatic HER2-receptive negative breast cancer patients with germline deletion in the cytosine deaminase (APOBEC3B) gene. Approximately 44 subjects will be enrolled in this study to examine the efficacy of pembrolizumab when given 200 mg intravenously (IV) every 3 weeks (Q3W) for up to 35 administrations (2 years). ER+ patients need to have failed at least one line of prior hormonal treatment. All patients need to have failed at least one line, but no more than 3 lines, of prior chemotherapy in the metastatic setting.

Disease status will be followed by imaging studies at 9 weekly interval ( $\pm$  7 days) during the first year, independent of any treatment delays, and every 12 weeks ( $\pm$ 7 days) after the first year, until disease progression, start of non-study treatment, withdrawal of consent to study participation, death or end of the study. RECIST 1.1 will be used as the primary efficacy endpoint of response rate. Safety will be monitored according to the National Cancer Institute Common Terminology Criteria for Adverse Events (CTCAE) Version 4.0.

Study treatment will continue until any of the following occurs:

1. Disease progression, as defined by Response Evaluation Criteria in Solid Tumour (RECIST version 1.1) (when progressive disease [PD] is confirmed, subject may be further followed up using consensus guideline of modified RECIST 1.1 [iRECIST] criteria);
2. Unacceptable toxicity;
3. Intercurrent illness that necessitates discontinuation of study treatment;
4. Investigator's decision to withdraw the subject,
5. Pregnancy;
6. Non-compliance with study treatment or procedure requirements;
7. Withdrawal of consent to treatment;
8. Death;
9. End of the study;
10. Other administrative reasons requiring cessation of study treatment.

This study will be conducted in conformance with Good Clinical Practices.

Specific procedures to be performed during the trial, as well as their prescribed times and associated visit windows, are outlined in the Trial Flow Chart - Section 6.0. Details of each procedure are provided in Section 7.0 – Trial Procedures.

Subject will be given a pre-screening informed consent form to participate in the genetic testing to determine their APOBEC3B germline mutation status.

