#### **5.4 Participant Withdrawal/Discontinuation Criteria**

Participants may discontinue study treatment at any time for any reason or be dropped from the study treatment at the discretion of the investigator should any untoward effect occur. In addition, a participant may be discontinued from study treatment by the investigator or the Sponsor if study treatment is inappropriate, the trial plan is violated, or for administrative and/or other safety reasons. Specific details regarding procedures to be performed at study treatment discontinuation are provided in Section 7.1.4 – Other Procedures.

A participant must be discontinued from study treatment but continue to be monitored in the study for any of the following reasons:

- The participant or participant's legally acceptable representative requests to discontinue study treatment
- Confirmed radiographic disease progression outlined in Section 7.1.2.6
- Any progression or recurrence of any malignancy, or any occurrence of another malignancy that requires active treatment
- Unacceptable adverse experiences as described in Section 5.2.2.
- The participant has a medical condition or personal circumstance which, in the opinion of the investigator and/or sponsor, placed the participant at unnecessary risk from continued administration of study treatment.
- The participant has a confirmed positive serum pregnancy test
- Noncompliance with study treatment or procedure requirements
- Recurrent Grade 2 pneumonitis
- Discontinuation of treatment may be considered for participants who have attained a confirmed complete response (CR) and have been treated for at least 8 cycles (at least 24 weeks), receiving at least 2 doses of pembrolizumab beyond the date when the initial CR was declared. These participants may be eligible for second course treatment described in Section 5.2.5.
- The participant is lost to follow-up
- Completion of 35 treatments (approximately 2 years) with pembrolizumab

Note: The number of treatments is calculated starting with the first dose. Participants who stop the combination or pembrolizumab after receiving 35 doses may be eligible for retreatment if they progress after stopping study treatment provided they meet the requirements detailed in Section 5.2.3. Participants may be retreated in the Second Course Phase (Retreatment) for up to an additional 17 cycles (approximately 1 year).

- Administrative reasons

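### The treatment rules at first RECIST 1.1 progression are inconsistent: for clinically stable patients the sections variously end treatment, advise against stopping, or leave it to discretion, and for unstable patients one sentence turns on an undefined term.

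*Protocol*

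**What the plan says.** **Clinically stable patients**

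- Protocol Sections 1.0 and 2.0 list the events that end treatment. Section 2.0 begins with "Disease progression, as defined by Response Evaluation Criteria in Solid Tumour (RECIST version 1.1", and Section 1.0 has the same item. In both, the parenthesis on iRECIST concerns further follow-up and does not mention continued dosing.
- Section 5.4 lists reasons for mandatory discontinuation. One is "Confirmed radiographic disease progression outlined in Section 7.1.2.6". The next is "Any progression or recurrence of any malignancy, or any occurrence of another malignancy that requires active treatment".
- Section 7.1.2.6.5 makes RECIST 1.1 the primary measure and uses it "as a basis for all protocol guidelines related to disease status (eg, discontinuation of study treatment").
- Section 7.1.2.6.6 says: "When clinically stable, participants should not be discontinued until progression is confirmed by the Investigator, working with local radiology, according to the rules below". Its next sentence opens with "This allowance to continue treatment despite initial radiologic PD", and the section ends by stating that "iRECIST will be used by the Investigator to assess tumour response and progression, and make treatment decisions".
- Section 7.1.2.6.2, the first row of Table 4 and Appendix 4 allow treatment to go on at the investigator's discretion until the repeat scan.

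**Clinically unstable patients**

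- Table 4 and Appendix 4 discontinue at the first radiologic evidence of progression.
- Section 7.1.2.6 keeps treatment going until the progression has been verified. It attaches no condition on clinical stability and does not say what verification consists of.

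**The concern.** These passages govern the same moment, the first scan that shows RECIST 1.1 progression, and they give different actions for the same patient. A site that follows Sections 1.0 and 2.0 stops. A site that follows the first sentence quoted from Section 7.1.2.6.6 does not. A site that follows Table 4 decides case by case.

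Three things are at stake:

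- **Exposure after progression.** It depends on which section a site treats as governing.
- **Coding.** Sections 8.3 and 8.7.2 summarise discontinuations by reason, and a monitor has to decide whether continuing past first progression is a deviation.
- **Safety.** The sentence in Section 7.1.2.6 could be taken to keep an unstable patient on drug when Table 4 and Appendix 4 would stop it.

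**Working it through.** The plan gives no figure to reproduce, so the main check is a comparison of the passages. A dose count then shows what hangs on the choice.

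**1. Stable patient at first RECIST 1.1 progression**

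- *Stop:* Sections 1.0 and 2.0. Section 7.1.2.6.5 gives weaker support, because it makes RECIST 1.1 a basis for discontinuation without saying that it is the only one.
- *Do not stop before confirmation:* Section 7.1.2.6.6, first sentence quoted.
- *Optional:* Section 7.1.2.6.2, Table 4 and Appendix 4. Section 7.1.2.6.6 also belongs here in part, since it refers to the rules that follow it and calls continuation an allowance.
- *Unclear:* Section 5.4. Its confirmed-progression item fits the optional reading. The item beside it mentions no confirmation, and its closing condition on active treatment may qualify the whole item or only its last part.

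No visible passage says that Table 4 or Appendix 4 overrides Sections 1.0 and 2.0, or that the advice against stopping gives way to discretion.

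**2. Unstable patient at first RECIST 1.1 progression**

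- *Stop:* Table 4 and Appendix 4.
- *Continue until verified:* Section 7.1.2.6. Its next sentence treats verification as separate from iRECIST confirmation, so the iRECIST rules in Appendix 4 do not supply the meaning.
- If verification means checking the same scan, any conflict is brief. If it means a repeat scan, the conflict lasts until that scan. The text does not decide between these.

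**3. Doses between the two actions for a stable patient**

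Inputs: a dose every 21 days (Table 1); first on-study scan at day 63 ± 7, that is days 56 to 70 (Section 7.1.2.6.2); confirmation 4 to 8 weeks later, that is 28 to 56 days (Section 7.1.2.6.2, Table 4).

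Assumptions: allocation and Cycle 1 Day 1 both fall on day 0, and the ±3-day dosing window is ignored.

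Count = number of dosing days 21k with scan day ≤ 21k < confirmation day.

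- All combinations: 15 scan days × 29 intervals = 435. The count is 1 dose in 78, 2 in 273 and 3 in 84 (78 + 273 + 84 = 435). These are not weighted by likelihood; only the range of 1 to 3 is used.
- Confirmation at 28 days: 1 or 2 doses. At 56 days: 2 or 3 doses.
- On schedule (scan on day 63, read before dosing), stopping leaves day 42 as the last dose.
  - Confirmation on day 63 + 28 = 91 adds doses on days 63 and 84. The last dose moves by 84 − 42 = 42 days, or 6 weeks.
  - Confirmation on day 63 + 56 = 119 adds doses on days 63, 84 and 105. The last dose moves by 105 − 42 = 63 days, or 9 weeks.
- If the day-63 dose is given before the scan, the two counts fall to 1 and 2.

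Three doses is not an upper limit. The third row of Table 4 lets a stable patient with persistent unconfirmed progression continue for another 4 to 8 weeks. With two intervals of 56 days the span is 112 days, and 112 / 21 = 5.3, so 5 or 6 doses.

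**The case against.** The strongest reply is that the protocol does point to a governing rule. Section 5.4 ties mandatory stopping to confirmed progression and sends the reader to Section 7.1.2.6. Section 7.1.2.6.6 defers to the rules after it, and Table 4 and Appendix 4 agree with each other: discretion if stable, stop if unstable. Section 2.0 refers procedural detail to Section 7.0. Sections 7.1.2.6.5 and 7.1.2.6.6 can be read in sequence, because Appendix 4 has no separate iRECIST assessment before RECIST 1.1 progression.

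Much of this stands. Discretion is the most likely intent, and Sections 7.1.2.6.5 and 7.1.2.6.6 on their own would be weak evidence of a conflict. It does not remove the difficulty. A general pointer to Section 7.0 for procedures is not a statement that Table 4 overrides the stopping rule in Sections 1.0 and 2.0, and those sections do not mention dosing beyond progression.

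A reader might infer more than the text supports in four places:

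- *That stopping a stable patient is forbidden, or would be a deviation.* Section 7.1.2.6.6 uses advisory wording and then speaks of an allowance. Sections 1.0 and 2.0 also list the investigator's decision to withdraw the subject, and Section 5.4 lets the investigator stop treatment judged inappropriate.
- *That Section 7.1.2.6 flatly contradicts Table 4 for unstable patients.* That depends on what verification means. Table 4 also lies within Section 7.1.2.6 and deals with these patients expressly.
- *That the contradiction causes 1 to 3 extra doses.* A purely discretionary rule would allow the same range.
- *That Figure 1 leaves the matter open too.* It is titled for clinically stable participants, but it is not shown in this copy and was not assessed. It could help with intent; it could not change the wording elsewhere.

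**Conclusion.** The inconsistency is real but narrower than a clash of three binding rules. For clinically stable patients two questions are unsettled: whether continuing past first progression complies with Sections 1.0 and 2.0, and whether the advice against stopping in Section 7.1.2.6.6 binds. For clinically unstable patients the extent of the conflict depends on the undefined term in Section 7.1.2.6.

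The RECIST 1.1 endpoints are largely unaffected, since the date of first RECIST 1.1 progression does not depend on which treatment rule is followed afterwards. The consequences lie in exposure after progression, the coding of discontinuations and deviations, and patient safety. The dose range of 1 to 3, or more with persistent unconfirmed progression, rests on the schedule assumptions given with the count. The number of patients affected cannot be derived from the protocol. No view is taken on which clinical rule is right.

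**What to change.** - Reconcile Sections 1.0, 2.0, 5.4, 7.1.2.6, 7.1.2.6.2, 7.1.2.6.5 and 7.1.2.6.6, Table 4 and Appendix 4, so that one sponsor-chosen rule for clinically stable patients and one for clinically unstable patients is stated in the same terms throughout. Alternatively, state which passage takes precedence.
- Define verification in Section 7.1.2.6 and say to which patients that sentence applies.
- In Section 5.4, make clear what the condition on active treatment qualifies.
- Clerical: replace the references in Sections 7.1.2.6.2 and 7.1.2.6.4 to Sections 9.2.1.6 and 9.1.2.6, which do not exist. Section 9 covers clinical supplies.

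The cost is an amendment of wording, with no added procedures or patients.
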